1. INTRODUCTION

This statistical analysis plan (SAP) for the 73763989HPB2004 phase 2 trial describes the statistical analyses and definitions to assess the efficacy and safety of the study intervention with JNJ-73763989 (100 mg every 4 weeks [Q4W]) and Nucleos(t)ide analogs (NA) in participants co-infected with hepatitis B virus (HBV) and hepatitis D virus (HDV). In this document the abbreviation JNJ-3989 is used to refer to the treatments JNJ-73763989. This SAP to be interpreted in conjunction with the clinical protocol amendment 4 finalized on 07 April 2023.

This is a 2-part, Phase 2, randomized, double-blind, placebo-controlled deferred active treatment, parallel, multicenter, interventional study comprising a proof-of-concept Part 1 followed by Part 2.

Part 1 will provide the data to evaluate the safety, tolerability, and HDV anti-viral activity signal of JNJ-3989+NA in a small number of participants (N=20), prior to enrolling a further number of participants in Part 2. The Part 2 of the study was originally planned with N = 145, however, as of protocol Amendment 4, sample size was reduced to 30 participants due to stopped enrollment. Monitoring of the safety and efficacy in terms of HDV RNA and HBsAg data in the JNJ-3989+NA arm aims to exclude futility of the regimen and initiate Part 2.

Part 2 will provide additional evidence of safety and efficacy of the JNJ-3989 regimen in the treatment of HBV/HDV co-infection.

An independent data monitoring committee (IDMC) will be commissioned for this study to monitor data on a regular basis to ensure the continuing safety, efficacy and well-being of the participants enrolled in this study (see Section 3.1).

Details of the pharmacokinetic (PK) and pharmacokinetic/pharmacodynamics (PK/PD) analyses will be described in a separate analysis and modeling plan.

1.1. Trial Objectives and Endpoints

Objectives	Endpoints
Primary	
To evaluate on-treatment efficacy against HDV of JNJ-3989 + NA regimen compared to NA alone.	
 Proportion of participants with HDV RNA $\geq 2 \log_{10}$ IU/mL decline from baseline or HDV RNA TND in combination with normal ALT at Week 48.
Key Secondary	
To evaluate on-treatment efficacy of the JNJ-3989 + NA regimen in suppressing HDV replication as measured by HDV RNA.	
 Proportion of participants with HDV RNA $\geq 2 \log_{10}$ IU/mL decline from baseline or HDV RNA TND at Week 48.
To evaluate efficacy of the JNJ-3989 + NA regimen on liver inflammation during study intervention phase.	
 Proportion of participants with normal ALT at Week 48.

Objectives	Endpoints
To evaluate the efficacy of the JNJ-3989 + NA regimen in terms of HBsAg response.	
 Proportion of participants with HBsAg seroclearance at Week 48.
To evaluate the efficacy of the JNJ-3989 + NA regimen on liver fibrosis.	
 Proportion of participants with ≥ 2 kPa reduction from baseline in liver stiffness measurement (LSM) assessed by vibration-controlled transient elastography (VCTE) (FibroScan) at Week 48.
Other Secondary	
To evaluate the efficacy of the JNJ-3989 + NA regimen during study intervention phase and follow-up phase.	
 Proportion of participants with HDV RNA $\geq 2 \log_{10}$ IU/mL decline from baseline or HDV RNA TND in combination with normal ALT. Proportion of participants with HDV RNA $\geq 2 \log_{10}$ IU/mL decline from baseline in combination with normal ALT. Proportion of participants with HDV RNA TND in combination with normal ALT. Proportion of participants with HDV RNA $\geq 2 \log_{10}$ IU/mL decline from baseline or HDV RNA TND. Proportion of participants with HDV RNA $\geq 2 \log_{10}$ IU/mL decline from baseline. Proportion of participants with HDV RNA TND. Proportion of participants with normal ALT. Time to reach HDV RNA $\geq 2 \log_{10}$ IU/mL decline or HDV RNA TND. Changes from baseline in HDV RNA. Changes from baseline in ALT.
To evaluate the safety and tolerability of the study intervention throughout the study.	
 Proportion of participants with incidences of (S)AEs and abnormalities in clinical laboratory tests (including hematology, blood biochemistry, blood coagulation, urinalysis, urine chemistry, and renal biomarkers), 12-lead ECGs, vital signs, and physical examination.
To evaluate the efficacy of the JNJ-3989 + NA regimen as measured by HBV blood markers (such as HBsAg, HBeAg*, HBV DNA) during study intervention and follow-up.	
 Proportion of participants with HBsAg seroclearance and/or seroconversion. Change from baseline over time in HBsAg, HBeAg*, HBV DNA. Proportion of participants with HBsAg, HBeAg*, and/or HBV DNA levels or changes from baseline below/above different cut-offs. Time to reach efficacy thresholds such as HBsAg < 1 IU/mL.

Objectives	Endpoints
To evaluate the frequency of HBV virologic breakthrough throughout the study.	
 Proportion of participants with HBV DNA virologic breakthrough.
To evaluate the PK of JNJ-3989 throughout the study.	
 PK parameters of JNJ-3989 (JNJ-73763924 and JNJ-73763976).
To evaluate changes in liver fibrosis during study intervention and follow-up.	
 Proportion of participants with ≥ 2 kPa reduction from baseline in Liver Stiffness Measurement (LSM) assessed by VCTE (FibroScan). Change from baseline in LSM over time assessed by VCTE (FibroScan).
To evaluate the anti-HDV efficacy during the follow-up phase.	
 Proportions of participants with sustained HDV response off-treatment post end of JNJ-3989 treatment. Proportions of participants with HDV relapse post end of JNJ-3989 treatment.
To evaluate the anti-HBV efficacy during the follow-up phase.	
 Proportions of participants with sustained HBV response off-treatment post end of JNJ-3989 treatment. Proportions of participants with HBV flare (virologic, biochemical, and clinical) post end of treatment.
Exploratory	
To explore the relationship between PK parameters (JNJ-3989) and selected pharmacodynamic (PD) parameters of efficacy and/or safety, as applicable.	
 Relationship between various PK parameters (JNJ-3989) and selected efficacy and/or safety endpoints, as applicable.
To explore the relationship between HBsAg and HDV RNA.	
 Correlation between HBsAg decline and HDV RNA levels/changes.
To explore the impact of the viral and host baseline characteristics on safety and efficacy.	
 Correlation of viral and host baseline characteristics (such as HBV/HDV genotype, baseline HBV DNA levels, baseline HDV RNA levels, age, sex, body mass index [BMI]) with selected efficacy and safety variables.
To explore the effect of any baseline variation in the HBV and HDV (if feasible) genome on efficacy.	
 Correlation of HBV and HDV genome sequence with selected efficacy parameters.
To explore changes in the HBV and HDV (if feasible) genome sequence during study intervention and follow-up.	
 Emergence of intervention-associated mutations.

Objectives	Endpoints
To explore efficacy as measured by HBV RNA and HbcrAg during study intervention and follow-up.	
 Changes from baseline in HBV RNA and HbcrAg levels. Time to reach undetectability of HBV RNA and HbcrAg.
To explore HBV-specific T-cell responses during study intervention.**	
 Changes from baseline in peripheral blood T-cell responses.
To explore medical resource utilization (MRU) to manage participants during study intervention and follow-up.	
 Number and type of medical visits. Number (proportion) of participants requiring hospitalization and duration of hospitalization (total days length of stay, including duration by wards; eg, intensive care unit (ICU)). Number and character of diagnostic and therapeutic tests and procedures.
To explore liver viral responses during study intervention.***	
 Changes from baseline in intrahepatic viral parameters (such as HDV RNA, HDAg, cccDNA, pgRNA, intrahepatic RNA, or HBsAg in terms of copy number, or number of positive cells). Changes from baseline in intrahepatic cccDNA. Levels and transcriptional activity (pgRNA/cccDNA ratio).
To explore liver immune responses during study intervention.***	
 Changes between baseline and on-treatment liver biopsy in intrahepatic immune response (eg, CD45+ T-cells, CD4+ T-cells, CD8+ T-cells, Natural Killer cells, and dendritic cells) in terms of proportion of cells, cell types, and spatial redistribution
To explore the relationship of intrahepatic markers with blood markers (immune and viral).	
 Association between levels and changes in intrahepatic and blood markers.

*: in HBeAg-positive participants only

** Peripheral blood mononuclear cell (PBMC) samples for immune analyses will be collected at selected sites only and as operationally feasible

*** If sufficient number of participants contribute to the liver biopsy collection

1.2. Trial Design

Prior Protocol Amendment #4 the study was planned to include 2 parts, Part 1 (approximately N=20) with proof of concept objectives and Part 2 (approximately N=145) with confirmatory objectives. As of Protocol Amendment #4, Part 2 sample size was reduced to 30 participants which triggered modifications of objectives of Part 2 from confirmatory to exploratory.

Part 2 of the study will only be initiated once the antiviral activity criteria in Part 1 have been met and after evaluation of the results of the first IA during the double-blind phase of Part 1. Cirrhotic participants will be excluded from participation in Part 2 of the study.

Each part includes 3 phases: a 4-week screening phase (may be extended up to a maximum of 6 weeks), 144-weeks study intervention phase (Arm 1) and 148-weeks study intervention phase (Arm 2), 48-week follow-up phase. The first 52 weeks of the intervention phase are double-blind followed by 96 weeks of open-label (OL) treatment.

In each part the participants will be randomized in a 4:1 ratio to Arms 1:2.

- Arm 1: 100 mg JNJ-3989 (subcutaneous [SC] injection every 4 weeks [Q4W]) + NA qd for 144 weeks;
- Arm 2: placebo for JNJ-3989 (SC injection Q4W) + NA qd for 52 weeks, followed by 100 mg JNJ-3989 (SC injection Q4W) + NA qd for 96 weeks (control deferred active treatment arm).

Randomization will be stratified by presence of compensated cirrhosis at screening (yes or no) (Part 1 only), HDV RNA testing laboratory location (China versus outside China) (all sites in China will utilize the laboratory testing in China and all sites in other countries will utilize the laboratory outside of China), and HBeAg status at screening (positive versus negative).

Prior Protocol Amendment #4, if safety was confirmed and futility excluded in Part 1, the total number of participants in this study was planned to be approximately 165 participants (specifically with a target of approximately 20 participants in Part 1, and 145 participants [up to a maximum of 170 participants] in Part 2), aged ≥ 18 to 65 years of age, co-infected with HDV and HBV. An interim analysis (IA) during DB study intervention phase was planned to re-assess the sample size in Part 2 and potentially increase it to maintain the statistical power at minimum at 80%. The maximum total sample size allowed for Part 2 of this study was 170. A reduction in sample size was not allowed, hence the minimum sample size for Part 2 was the planned number of 145 participants (see Section 1.4). The confirmatory conclusions of the study would be based on data from Part 2 only (145 participants, or, if recommended by IDMC, up to 170 participants). As Per Protocol Amendment #4, the total sample size of the study is 52, with 22 participants in Part 1 and 30 participants in Part 2. Data from Part 1 and Part 2 will be reported both separately and together to contribute to the overall benefit/risk ratio assessment of the regimen.

1.3. Statistical Hypotheses for Trial Objectives

The original protocol had as primary hypothesis of this study that the combination regimen of JNJ-3989 + NA has superior efficacy compared to NA treatment alone in reducing HDV replication and improving the associated liver inflammation, as measured by the primary efficacy endpoint at Week 48 (the proportion of participants with HDV RNA decline ≥ 2 log₁₀ IU/mL from baseline or HDV RNA TND in combination with normal ALT at Week 48). Due to the decision to stop enrollment at 30 participants in Part 2 of the study (see Section 1.2), the primary study hypothesis can no longer be tested with sufficient power, and hence the statistical analyses will be descriptive.

1.4. Sample Size Justification

A total sample size of 130 participants for Part 2 in the original protocol would have yielded a statistical power >90% to detect a between-arm difference of $\geq 26\%$ in the primary efficacy endpoint at Week 48, at a 1-sided Type 1 error rate of 0.025, based on the test for the between-arm difference in proportions with the normal approximation. Per Protocol Amendment 4, the sample size in Part 2 was reduced to 30 participants. In the original protocol, sample size re-estimation was planned at the single IA during Part 2 to allow for an increase to a maximum of 170 participants in Part 2 for the conditional power at the end of the study to be at least 80% in case the assumed 0.04 response rate for placebo was too conservative. Due to reduction in sample size per Protocol Amendment 4, the single IA with sample size re-estimation was removed. In the original protocol, the number of participants included in this study was planned to be a minimum of approximately N=20 (if Part 2 is not initiated) or between a minimum of N=165 and a maximum of N=190 if Part 2 is initiated. Per Protocol Amendment 4, the planned number of participants included in the study will be N=20 in Part 1 and N=30 in Part 2.

1.5. Randomization and Blinding

Randomization and Stratification

Randomization will be performed using a 4:1 ratio (Active regimen from the start Arm1 : Placebo/deferred treatment Arm 2), regardless of the study part, to minimize bias in the assignment of participants to intervention arms, to increase the likelihood that known and unknown participant attributes (eg, demographic and baseline characteristics) are evenly balanced across treatment arms, and to enhance the validity of statistical comparisons across intervention arms.

Randomization will be stratified by presence of compensated cirrhosis at screening (yes or no) (Part 1 only), HDV RNA testing laboratory location (China versus outside China), and HBeAg status at baseline (positive versus negative) in order to provide an evenly balanced representation across the 2 arms.

Blinding

Blinded treatment will be used to reduce potential bias during data collection and evaluation of clinical endpoints.

The investigators, participants and all site personnel will remain blinded to study intervention allocation until Week 52 (Part 1) and Week 48 (Part 2). After Week 52 (Part 1) and Week 48 (Part 2), it will be communicated to the investigators whether the participants were allocated to either the investigational arm (Arm 1) or the control arm (Arm 2) to allow the correct open-label and follow-up visits schedule to be followed (see Schedules of Activities). For each participant, all HDV RNA, HBsAg, HBeAg, HBcrAg, anti-HBs, and anti-HBe antibody testing individual results will be provided to the investigator and the sponsor for managing the participant's safety.

After Week 52 and up and until Week 144, study intervention will be administered in open-label fashion to all participants (except Part 2 participants allocated to Placebo+NA who had HBsAg >10,000 IU/mL at screening or baseline).

Prior to Part 1 IA1 (see Section 3.3.2.1.1), the Sponsor Committee will review unblinded aggregated interim data of HDV RNA, HBsAg, ALT, AST, total and direct bilirubin, HBV DNA and individual patient profiles for the values/changes from baseline over time for all participants in Part 1 including those randomized to the placebo+NA arm.

Part 1 IA1 will include the review of all unblinded efficacy and safety results by the Sponsor Committee and the decision whether the Part 2 can be initiated based on the review of the antiviral activity criteria in conjunction with ALT elevations and other safety data, taking into consideration the IDMC recommendations. From the moment of unblinding for this IA onwards, the Sponsor Committee will remain unblinded to Part 1 data.

The Study Team will become unblinded at the time of the IA1 of Part 1, throughout IA2 of Part 1 until completion of Part 1, but will remain blinded to all data of Part 2 until the end of double-blind phase (each individual participant will be unblinded after they reach Week 48 or discontinue earlier).

2. GENERAL ANALYSIS DEFINITIONS

The SAP will use throughout the document the following definitions:

- Study treatment refers to: JNJ-3989, placebo, or NA [entecavir (ETV), tenofovir disoproxil (TD), or tenofovir alafenamide fumarate (TAF)]
- Study agent refers to: JNJ-3989 or placebo
- Study intervention arm refers to:
 - Arm 1: JNJ-3989 (100 mg) + NA
 - Arm 2: Placebo + NA

2.1. Analysis Phases and Visit Windows

2.1.1. Analysis Phase

The analysis phases are defined in [Table 1](#) below.

Table 1: Analysis Phases Start and End Dates

Analysis phase	Start date	End date
Screening	The date of signing the informed consent	1 day before the first study agent intake
Double-Blind (DB) Study Intervention	Date of first study agent intake	
If participant did not withdraw from the study and did not discontinue treatment early prior to the projected/actual Week 52 Visit date:
 
Min(Date of Week 52 study agent intake – 1 day, cut-off date*)
 
Otherwise:
 
[Min (Early study withdrawal visit date, study agent discontinuation date) + 5 days^a] or cut-off date*, whichever occurs first

Open-Label (OL) Study Intervention	
If participant has a projected/actual Week 52 Visit date:
 
 – End date of DB study intervention phase + 1 day 
Otherwise:
 
 – Missing 	
If participant did not withdraw from the study prior to the projected/actual Week 144 (Arm 1)/Week 148 (Arm 2) Visit date and did not discontinue treatment early prior to the projected/actual Week 140 (Arm 1)/Week 144 (Arm 2) Visit date:
 
[Min (Date of Week 144 Visit (for Arm 1) or / Date of Week 148 Visit (for Arm 2))+ 5 days^a] or cut-off date*, whichever occurs first
 
if participant withdrew from the study or discontinued treatment between projected/actual Week 52 Visit date + 1 day and projected/actual Week 144 (Arm 1)/Week 148 (Arm 2) Visit date:
 
[Min (Early study withdrawal visit date, study agent discontinuation date)+ 5 days^a] or cut-off date*, whichever occurs first

Follow-up	
If participant did not withdraw informed consent during DB or OL study intervention phases
 
Max (End date of DB study intervention phase, End date of OL study intervention phase) + 1 day
 
Otherwise:
 
Missing
	
If participant entered the Follow-up phase:
 
Max [early study withdrawal visit date, study completion date] or cut-off date, whichever occurs first.
 
Otherwise:
 
Missing

*Cut-off dates will be defined to match the prespecified timepoints for IDMC safety monitoring, interim analysis, the primary analysis and the final analysis, respectively.

^a: Addition of 5 days is only applicable for Adverse Events and Concomitant Medications

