2.1.3. Analysis Visits and Time Points

All visits for all assessments (safety, efficacy or PK) will be uniquely allocated within each phase to an analysis time point based on the analysis relative day (ADY) compared with the target days based on [Table 2](#). All assignments will be made in chronological order. Once a visit is assigned to a visit window (time interval in [Table 2](#)), it will no longer be used for a later time point except for the end of treatment (EOT) and the end of study (EOS) visits. If two or more visits fall within the same interval in the same phase, only one measurement will be selected for the analysis time point per phase in order to have only one evaluation per participant. The following rules will be applied:

1. The measurement closest to the target day in that phase will be used.
2. If the measurements fall equidistant from the target day, the last measurement in chronological order within the interval will be used per phase.
3. If there are two or more measurements on the same day, then the last measurement in chronological order will be used. If the time of the assessment is not available the highest record/sequence number will be selected.

The listings will include all measurements, also those multiple assessments within the same visit window/phase.

End of treatment (i.e. EOT) and end of study (i.e. EOS) time points will be included in all analysis over time unless stated otherwise.

Note: For the selection of the patient-reported outcome (PRO) measurements the above algorithm needs to be performed on the entire questionnaire (filled in at a specific date and time) and not on the individual questions /items (i.e., not mixing answers from different questionnaires)

Table 2 provides the analysis time points, time intervals for each visit per analysis phase.

Table 2: Analysis Time Point and Time Intervals by Analysis Phase

Phase	Target day	Analysis time point (Week)	Analysis time point (label)	Time interval (days) for Arm 1	Time interval (days) for Arm 2 ^(a)
Screening	-28 to -1	-1	Screening	<0	
Double-Blind (DB) Study Intervention	1	0	Baseline	Pre-dose ; 1	
	15	2	Week 2	[2,22]	
	29	4	Week 4	[23, 43]	
	57	8	Week 8	[44, 71]	
	85	12	Week 12	[72, 99]	
	113	16	Week 16	[100, 127]	
	141	20	Week 20	[128, 155]	
	169	24	Week 24	[156, 183]	
	197	28	Week 28	[184, 211]	
	225	32	Week 32	[212, 239]	
	253	36	Week 36	[240, 267]	
	281	40	Week 40	[268, 295]	
	309	44	Week 44	[296, 323]	
	337	48	Week 48	[324,351]	

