4.6. Extent of Exposure

Extent of exposure to study treatments will be summarized and presented based on the safety analysis set. The total duration of exposure during the DB and OL study intervention phases will

be calculated by each study treatment (JNJ-3989/placebo and NA) separately and summarized descriptively by intervention arm. The duration of treatment with NA will be summarized also for the follow up phase for participants with presence of compensated cirrhosis at screening by intervention arm.

Because of the different route and frequency of treatment administration across the 2 study treatments (for JNJ-3989/placebo one subcutaneous injection once every 4 weeks, and for NA once daily tablet), the total duration of exposure (weeks) will be calculated by analysis phase for each agent as follows:

- For the DB study intervention phase:
 - JNJ-3989/placebo: $[\text{Min} ((\text{Date of last injection in the DB intervention phase} + 27 \text{ days}), \text{Early study withdrawal visit date, cut-off date}) - \text{date of first injection in the DB phase} + 1] / 7$
 - NA: $[\text{Min} (\text{Date of the last NA administration in the DB phase, Date of discontinuation from NA, Early study withdrawal visit date, cut-off date}) - \text{first drug administration date in the DB phase} + 1] / 7$
- For the OL study intervention phase (only for participants with non-missing OL phase start date, as defined in Section 2.1.1):
 - JNJ-3989: $[\text{Min} ((\text{Date of last injection in the OL phase} + 27 \text{ days}), \text{Early study withdrawal visit date, cut-off date}) - \text{Week 52 study agent intake date} + 1] / 7$
 - NA: $[\text{Min} (\text{Date of the last NA administration in the OL phase, Date of discontinuation from NA, Early study withdrawal visit date, cut-off date}) - \text{Week 52 NA intake date} + 1] / 7$

Cutoff dates will be defined to match the prespecified timepoints for IDMC periodical data reviews, interim analyses and the primary and final analyses, respectively (see Section 3.3).

The number and percentage of participants who skipped any dose of JNJ-3989/placebo or NA will be summarized separately for each study treatment by intervention arm during the DB and OL study intervention phases, separately. Additionally, the number and percentage of participants who missed 2 or more consecutive JNJ-3989/placebo injections, or who missed more than 5 doses of NA within a four-week period will be presented.

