4.7. Treatment Compliance

Treatment compliance will be summarized for the safety analysis set by intervention arm for each study treatment except NA.

DB Treatment compliance (%) is defined as follows.

For JNJ-3989/placebo: (Total number of injections received/ 13) * 100%

OL Treatment compliance (%) is defined as follows.

For JNJ-3989 in Arm 1: (Total number of injections received/ 23) * 100%

For JNJ-3989 in Arm 2: (Total number of injections received/ 24) * 100%

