5.5.1.4. Additional Efficacy Endpoints Relative to The Actual Duration of JNJ-3989 Treatment

This section intends to evaluate some selected efficacy endpoints over time conditional upon the same treatment duration with JNJ-3989 across the 2 arms based on Part 2 data. For example, DB

Week 24 for Arm 1 corresponds to Week 76 for Arm 2 (Week 52+24, See [Table 2](#)), as participants in Arm 2 start treatment with JNJ-3989 at Week 52 when they switch over to the active regimen. For each DB Week X for Arm 1 data, the corresponding Week 52+X for Arm 2 data will be considered, as described in [Table 5](#):

Table 5: Correspondence between timepoints for Arm 1 and Open Label timepoints for Arm 2

Analysis Time point for Arm 1 (label)	Matching Analysis OL Timepoint for Arm 2 (label)
Baseline	Week 52
Week 2	Week 54
Week 4	Week 56
Week 8	Week 60
Week 12	Week 64
Week 16	Week 68
Week 20	Week 72
Week 24	Week 76
Week 28	Week 80
Week 32	Week 84
Week 36	Week 88
Week 40	Week 92
Week 44	Week 96
Week 48	Week 100
Week 52	Week 104
Week 56	Week 108
Week 60	Week 112
Week 64	Week 116
Week 68	Week 120
Week 72	Week 124
Week 76	Week 128
Week 80	Week 132
Week 84	Week 136
Week 88	Week 140
Week 92	Week 144
Week 96	EOT (only for OL completers)

When applicable, the reference timepoint (RT) for those analyses will be baseline (DB Day 1) for Arm 1 and Week 52 for Arm 2.

The following endpoints will be presented for those time points during the open-label phase in Arm 2 that match the treatment duration in Arm 1 during the double-blind phase, because of the deferred active trial design, as per [Table 5](#).

The selected endpoints are:

- Proportion of participants with HDV RNA $\geq 2 \log_{10}$ IU/mL decline from RT or HDV RNA TND in combination with normal ALT
- Proportion of participants with HDV RNA $\geq 2 \log_{10}$ IU/mL decline from RT or HDV RNA $<$ LLOQ in combination with normal ALT

- Proportion of participants with HDV RNA $\geq 2 \log_{10}$ IU/mL decline from RT or HDV RNA TND
- Proportion of participants with HDV RNA TND
- Proportion of participants with HDV RNA <LLOQ
- Proportion of participants with normal ALT
- Proportion of participants with LSM reduction ≥ 2 kPa from RT
- Proportion of participants with HBsAg seroclearance i.e. with HBsAg < LLOQ, with HBsAg < 1 IU/mL and < 10 IU/mL
- Change from RT in HDV RNA
- Change from RT in ALT
- Change from RT in HBsAg
- Change from RT in LSM

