For each lab parameter, a worst-case analysis will be performed by using the worst abnormality and/or worst toxicity grade lab value and time point per participant. The worst toxicity case is the value associated to the highest toxicity grade and is derived per parameter and toxicity direction (low / high). Worst-case will be derived within each phase, including unscheduled assessments. For abnormalities, in case the same subject has both abnormalities (low and high) for the same lab test within the same phase, the participant will be counted in the analysis for both toxicity directions (abnormally high and low).

Imputation rules:

In case continuous laboratory results are not numerically expressed, but as a character (e.g. ‘less than 2’, ‘>25’), these results will be numerically imputed as follows:

- If the analysis result contains '<' then the result will be multiplied by 0.999 (e.g. <6.1 becomes 6.0939).
- If analysis result contains '>' then the result will be multiplied by 1.001 (e.g. >6.1 becomes 6.1061).
- If analysis result contains '≤' or '≥' then only the numeric portion of the result will be used.

This also applies to normal limits expressed as such.

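### Week 52 assessments go to the open-label phase with no pre-dose rule, although the SAP also uses Week 52 as Arm 2's pre-JNJ-3989 reference, and the double-blind end date is undefined without a Week 52 injection

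*SAP*

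**What the plan says.** For participants who reach Week 52 on treatment, Table 1 (SAP Section 2.1.1) ends the double-blind (DB) phase at "Min(Date of Week 52 study agent intake – 1 day, cut-off date" and starts the open-label (OL) phase at "End date of DB study intervention phase + 1 day". The first OL day is thus the calendar date of the Week 52 injection ("Date of Week 52 study agent intake").

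In Table 2 (Section 2.1.3) the last DB row is Week 48, days 324 to 351. Week 52, target day 365 and window 352 to 372, is the first OL row. Visits are "uniquely allocated within each phase to an analysis time point based on the analysis relative day (ADY").

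Section 5.5.1.4 says that "participants in Arm 2 start treatment with JNJ-3989 at Week 52 when they switch over to the active regimen". Table 5 pairs Arm 2's Week 52 with Arm 1's Baseline and makes it Arm 2's reference timepoint.

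For laboratory data, Section 6.2.1 says "Worst-case will be derived within each phase, including unscheduled assessments"; Sections 6.4.1 and 6.5.1 do the same for ECG and vital signs. Treatment emergence is judged against baseline, which Section 2.2 places before the first study treatment. The Week 52 reference is reserved for selected efficacy endpoints.

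Section 4.6 foresees missed doses ("The number and percentage of participants who skipped any dose of JNJ-3989/placebo or NA will be summarized separately") but starts OL exposure at the Week 52 intake date. Section 1.5 and the Amendment 5 rationale state that Part 2 placebo participants with HBsAg above 10,000 IU/mL at screening or baseline do not roll over to OL.

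**The concern.** The SAP gives one assessment two meanings. In Section 5.5.1.4 the Week 52 value is Arm 2's state before any JNJ-3989. In every analysis built by phase it is OL data, that is, data from the period when Arm 2 receives JNJ-3989. An Arm 2 abnormality that arose on placebo and was seen only at Week 52 would be missing from the DB tables and tabulated under open-label JNJ-3989. ALT elevation is the main safety question in this trial and Arm 2 is very small, so a single misplaced case is visible.

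The boundary also depends on an injection that some participants will not receive. For them the plan does not say when DB ends.

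**Working it through.** **1. The SAP's own day counts.** Target day = 7 × week + 1. Week 48 gives 337 and Week 52 gives 365, as in Table 2. Injections every 4 weeks from Week 0 to Week 48 number 48/4 + 1 = 13, which matches the DB compliance formula in Section 4.7 ("Total number of injections received/ 13) * 100"). Weeks 52 to 140 give (140 − 52)/4 + 1 = 23 for Arm 1 and Weeks 52 to 144 give 24 for Arm 2, also as stated. The thirteenth and last DB injection is therefore at Week 48, and its 4-week interval ends on day 337 + 27 = 364.

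**2. The boundary.** With dosing on day 365, DB ends on day 364 and OL starts on day 365. A pre-dose assessment on day 365 follows 364 days of placebo and no JNJ-3989 in Arm 2, yet it is OL. The same holds for any same-day assessment with the injection between days 352 and 372.

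**3. The window gap.** DB windows stop at day 351 while the phase runs to the day before the injection:

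- injection on day 352: 351 − 351 = 0 DB days without a window;
- injection on day 365: 364 − 351 = 13 days;
- injection on day 372: 371 − 351 = 20 days.

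Because allocation is within phase, a visit in this gap has no DB time point. That includes a Week 52 visit held before the injection date, or a Week 48 visit at least 352 − 337 = 15 days late.

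**4. Which analyses change.** The DB-phase repeated-measures models for HDV RNA, ALT, HBsAg and HBV DNA (Sections 5.5.2.2.1 to 5.5.2.2.3) exclude Week 52. The by-phase worst-case and treatment-emergent tables for laboratory tests, ECG and vital signs count it in OL.

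**5. Size in Arm 2.** At 4:1, Arm 2 is about 22/5 = 4.4 participants in Part 1 plus 30/5 = 6 in Part 2, or 52/5 = 10.4. Fewer enter OL because of the HBsAg exclusion. For an abnormality at Week 52 that is worse than the Day 1 baseline:

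- if it is also seen at a later OL visit, it counts as OL treatment-emergent under either rule, and the OL count does not change;
- if it is seen at Week 52 and not again, the current rule adds one participant to the OL count; if it was also not seen earlier, DB loses it.

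One participant in 10 is 10 percentage points. The SAP gives no rate for the second case.

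**6. No Week 52 injection.** Table 1 selects its branch by the projected or actual Week 52 visit date, but the end date itself needs an intake date. For the Part 2 placebo participants who do not roll over there are three readings. The minimum may be undefined. It may reduce to the cut-off date, so that follow-up data fall in DB. Or the planned stop may be treated as early discontinuation, which moves the participant to the other branch. The SAP does not choose. Someone who misses the Week 52 injection but continues has the same problem, and the OL exposure formula in Section 4.6 then has no start date.

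**The case against.** The strongest reply is that little depends on this boundary. The primary and key secondary endpoints are at Week 48. Between-arm differences in binary secondary endpoints are given at all time points (Section 5.5.2.1), and time-to-event endpoints are not split by phase (Section 5.5.1.3.1). Week 52 has its own labelled row. Safety is descriptive. DB worst-case tables include unscheduled assessments up to the end of the phase, and listings show every measurement. All of this stands and limits the point to the analyses in step 4.

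A reader might infer that Week 52 is lost from the double-blind comparison. The SAP does not support that. The Week 52 contrasts just named remain, and in Part 2 the arm is communicated to sites after Week 48 (Section 1.5), so Part 2 Week 52 values are not fully blinded whichever phase they are placed in.

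It is also fair that pre-dose sampling at Week 52 is inferred from Table 5 and not stated. The inference is strong, since the value could not otherwise match Arm 1's Baseline.

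Finally, a date-level boundary follows the SAP's convention at Day 1. There, however, Table 2 has a pre-dose row and Section 2.2 uses date and time of first administration. Week 52 has no equivalent.

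**Conclusion.** The point holds as an inconsistency in phase assignment, with limited consequences. As written, Week 52 values reflecting 52 weeks of placebo enter the OL safety tables and drop out of the DB-phase models. The effect on OL counts lies between none and a few participants among at most about 10. Only abnormalities not seen again after Week 52 alter whether a participant is counted.

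A reader might want to state a specific inflated OL incidence. That would need rates of transient abnormality on placebo and of true OL incidence, which the SAP does not give. A reader might also infer that a missed Week 52 injection would put a long stretch of active treatment into the placebo column. That presumes the minimum resolves to the cut-off date, which the SAP does not say. What the document supports is that the end date is undefined, and that a group for whom this matters exists by design.

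The conclusion assumes that Week 52 assessments are taken before the injection.

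**What to change.** 1. **Table 1:** assign Week 52 assessments taken before the first OL injection to DB, using date and time. If the time is missing, assign the scheduled Week 52 visit assessments to DB.
2. **Table 2:** add a DB Week 52 row from day 352 to the pre-dose assessment on the switch day, and start the OL rows after it. Flag Part 2 values as collected after the arm was disclosed at Week 48. Keep the same value as Arm 2's reference timepoint, and amend the Table 5 label, which now calls it an OL time point.
3. **No Week 52 injection:** end DB just before the first OL injection, or at the actual or projected Week 52 visit date if there is none. Use the first OL injection as the OL exposure start in Section 4.6. Set the OL start to missing for participants who never receive an OL injection, so that their later data fall in follow-up.

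The cost is SAP wording and minor reprogramming of the phase derivation; no new data are needed. The drawback is that Part 2 Week 52 values in DB tables are not fully blinded, hence the flag.
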